**[[contact]](mailto:[contact])**

**Statistical Plan on page 8**

## AIMS and HYPOTHESES

The assessment and treatment of chronic pain (CP) and Posttraumatic Stress Disorder (PTSD) are national priorities for the National Institute of Health (NIH) and the Veterans Health Administration (VHA) as we continue to see steep increases in the prevalence of these conditions among returning Veterans as well as relatively high rates of these conditions among civilians. Our laboratory has developed a rigorous, individually tailored, 3-month progressive exercise training program that appears to modify a key factor (neuropeptide Y: NPY) involved in the pathogenesis of CP and PTSD. Preliminary data suggest that progressive exercise-training induced changes in NPY system function were associated with improvements in PTSD, depression and pain-related interference and sensitivity, as well as intrinsic motivation to exercise. The proposed R21 will extend this research to examine the relationship between progressive exercise-training induced changes in NPY and the capacity for reward and self-regulation. These latter capacities are thought to be essential to intrinsic and extrinsic motivation and self-efficacy, which are known to promote long-term exercise maintenance, which is critical for long-term health maintenance. Findings from the study are therefore expected to inform development of more effective therapeutic interventions for CP/PTSD aimed at forestalling serious long-term disability and reliance on pharmacological interventions with high potential for abuse, dependence, and morbidity. In the proposed study, we will investigate the association between changes in key biological and neuropsychological factors induced by a rigorous, 3-month individually tailored, progressive exercise training program and achievement of exercise maintenance in a CP/PTSD population.

**Aim 1.** Evaluate whether changes in neuropeptide Y (NPY) system function correlate with changes in self-regulation and reward across the rigorous 3-month individually tailored, progressive exercise training program.

**Hypothesis 1a:** Pre-training resting plasma NPY levels will correlate with capacities for self-regulation and reward.

**Hypothesis 1b:** Changes in resting plasma NPY levels and the release of NPY in response to standardized cardiopulmonary exercise testing (CPX) conducted before and after a 3-month progressive exercise-training program will correlate with improvements in self-regulation and reward sensitivity.

**Aim 2.** Evaluate whether changes in NPY correlate with changes in self-efficacy and intrinsic motivation for exercise in response to a rigorous 3-month individually tailored, exercise-training program.

**Hypothesis 2a:** At baseline, acute exercise-induced increases in plasma NPY during CPX will correlate with exercise-related self-efficacy and intrinsic motivation to exercise.

**Hypothesis 2b:** The release of NPY during CPX will increase in response to the 3-month exercise-training program and correlate with increases in self-efficacy and intrinsic motivation to exercise.

**Aim 3.** Determine whether capacities for self-regulation and reward sensitivity, as well as self-efficacy and intrinsic motivation for exercise change in response to the 3-month exercise-training program and predict exercise maintenance.

**Hypothesis 3:** At endpoint, the factors under investigation will significantly predict exercise maintenance.

**Aim 4.** Evaluate whether changes in NPY system function across the 3-month exercise-training program correlate with improvements in pain sensitivity and interference, as well as depressive and PTSD symptoms.

**Hypothesis 4a:** At baseline, CPX-induced increases in plasma NPY will not correlate with pain-related interference and sensitivity, depression or PTSD severity.

**Hypothesis 4b:** At endpoint, CPX-induced increases in plasma NPY will correlate with reductions in pain-related interference and sensitivity, as well as with reductions in depression and PTSD symptoms.

Current effective treatments for CP/PTSD are limited. In addition, the treatment of CP and PTSD, which are commonly comorbid conditions, is typically undertaken by different clinical specialists working in separate specialty clinics. In contrast, this study is predicated on evidence suggesting that CP/PTSD comorbidity is mediated at least in part by common underlying pathophysiological factors. This study thus focuses on modification of one such biological factor that contributes to both CP and PTSD, and will provide valuable information about possible inter-related neurobiological and neuropsychological benefits of progressive exercise in veterans and civilians with CP/PTSD. This work may also serve as a foundation upon which innovative adjunctive treatments for CP/PTSD or other alternatives to current treatments for these disorders can be developed. For example, findings may lead to refinement of exercise behavior change protocols to fit the unique needs of this complex population and foster long term exercise maintenance. In addition, increased understanding of the neurobiological mechanisms of a successful exercise training intervention that leads to exercise maintenance may stimulate development of other epigenetic or pharmaceutical means of modifying biological factors key to the efficacy and maintenance of such treatments.

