### Statistical Analysis Plan

**Power and Sample Size Considerations:** Power calculations were carried out based on our recently published study which measured NPY, at baseline and peak time-points, in response to a single cardiopulmonary exercise stress test (CPX). Achievement of a Cohen’s d effect size of .5 will suggest statistically and clinically significant effects of the treatment within the CP/PTSD group. Thus, in order to obtain a power of 80% at the 5% level of significance a sample size of 30 participants will be required.

**Data Analyses:** Baseline demographics and descriptive variables (e.g., age, gender, pain duration) will be summarized. Descriptive summaries for continuous variables will be presented in terms of means and standard deviations while discrete variables will be summarized in terms of relative frequencies and percentages.

**Aims 1-2 &4:** The hypotheses under Aims 1, 2 and 4 will be evaluated using unconditional latent growth models (LGMs). The approach does not assume a linear trajectory and is thus ideal for this proposal. The intercept of the LGM will be centered on the baseline self-report data (i.e., first slope loading will be fixed to 0.0). The intermittent time point (midpoint) will be freely estimated, and the final post-training time point will have a corresponding slope factor loading fixed to 1.0. Accordingly, the mean and variance of the slope factor will convey the fixed (average) and random effects (individual differences) of change across exercise training. Effects of the exercise program will be evidenced by a significant slope factor mean (indicating significant change in the metric of interest). A significant slope variance will indicate individual differences in change across training and support further investigation of predictors of the variability.

**Aim 3:** At both CPX testing time-points, the putative mechanisms under investigation (reward, self-regulation, exercise-based SE and IM) will be correlated with each other using Pearson or Spearman correlations, as appropriate. Based on these findings, these putative psychological mechanisms will be entered as predictors in a discriminant function analysis to predict exercise maintenance.

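### The SAP's growth models contain no NPY term, so they cannot test Hypotheses 4a or 4b, and 4b leaves open whether endpoint release or change in release is meant

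*Combined protocol and SAP*

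**What the plan says.** In AIMS and HYPOTHESES, Aim 4 is to "Evaluate whether changes in NPY system function across the 3-month exercise-training program correlate with improvements in pain sensitivity and interference", and the same for depressive and PTSD symptoms. Two hypotheses follow. 4a: "At baseline, CPX-induced increases in plasma NPY will not correlate with pain-related interference and sensitivity, depression or PTSD severity". 4b: "At endpoint, CPX-induced increases in plasma NPY will correlate with reductions in pain-related interference and sensitivity", and with reductions in depression and PTSD symptoms.

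The Statistical Analysis Plan gives one method: "The hypotheses under Aims 1, 2 and 4 will be evaluated using unconditional latent growth models". On its form it says "The intercept of the LGM will be centered on the baseline self-report data" and "The intermittent time point (midpoint) will be freely estimated", with the post-training loading fixed at 1. A training effect is judged by the slope mean. A significant slope variance is said only to justify a later search for predictors, none of which is named.

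NPY release needs a cardiopulmonary exercise test (CPX). The schedule in APPROACH has CPX columns at baseline and post-training only. The Cold Pressor Test section says the midpoint session omits the CPX, and the compensation paragraph in section 8.2b counts two CPX sessions in total.

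The only power statement is for a Cohen's d of 0.5 within the group. No correlation is powered, and 4a has no equivalence bound or interval criterion.

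**The concern.** Both hypotheses are about a correlation between NPY release and symptoms. An unconditional growth model has no predictors, and the one described has no NPY variable. It can show that symptoms changed and that people differed in how much. It cannot show that either is related to NPY. Release cannot be the modelled variable either, because the model needs three time points and release has two. The sentence quoted above also covers Aims 1 and 2, so the release parts of those aims have the same gap.

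The analyst must therefore choose the test, and 4b does not say which to choose. Read literally, it pairs the response at the final visit with symptom reduction, so a participant whose release was high and never changed counts in its favour. Aim 4 asks about change. The companion hypotheses lean towards change: 1b begins "Changes in resting plasma NPY levels and the release of NPY in response to standardized cardiopulmonary exercise testing (CPX) conducted before and after", and 2b says "The release of NPY during CPX will increase in response to the 3-month exercise-training program and correlate with increases". The Preliminary Data section reports both post-training levels and change-with-change correlations, so either could be picked once results are known.

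Two things are at stake. A positive 4b could reflect a stable trait and be reported as a training mechanism. An imprecise null for 4a could be taken as the predicted absence.

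**Working it through.** **1. The plan's own figure.** A paired mean change with d=0.5, two-sided 5% and 80% power gives n = ((1.960+0.842)/0.5)² = 31.4, so 32. Power at n=30 is 78.2% by the normal approximation (75.4% by paired t). The stated 30 is thus roughly reproduced, but for a mean change. It does not cover a correlation.

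**2. Inputs for the correlations.** From the SAP: n=30 and 5% significance. Assumed, because the documents give no value: two-sided tests, a driving correlation of 0.5, and a pre-post correlation of release ρ of 0.3, 0.5 or 0.7. SDs are equal at the two visits and there is no assay error unless stated.

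Power by Fisher z: Φ(atanh(r)·√27 − 1.960). At r=0.5 this is Φ(2.854−1.960) = 81%, the best case for change with change. The critical |r| is 0.361, and the smallest r with 80% power is 0.49.

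**3. The two readings of 4b under three assumed truths.**

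- A. Improvement tracks stable release (the mean of both visits) and not its change: endpoint r = 0.5·√((1+ρ)/2).
- B. Improvement tracks only change in release: endpoint r = 0.5·√((1−ρ)/2).
- C. Change correlates 0.5 with improvement and baseline release is unrelated to it: endpoint r = 0.5·√(2(1−ρ)).

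| Truth | Endpoint r (ρ = 0.3 / 0.5 / 0.7) | Endpoint release significant | Change with change significant |
|---|---|---|---|
| A | 0.403 / 0.433 / 0.461 | 60% / 67% / 74% | 5% |
| B | 0.296 / 0.250 / 0.194 | 35% / 26% / 18% | 81% |
| C | 0.592 / 0.500 / 0.387 | 94% / 81% / 57% | 81% |

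Worked cell (B, ρ=0.3): √(0.7/2) = 0.592; times 0.5 = 0.296; atanh = 0.305; times √27 = 1.585; Φ(1.585−1.960) = 35%.

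Under B, an endpoint SD of 1.25 to 1.5 times baseline raises the endpoint figures to between 37% and 58%.

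**4. Assay error.** With release reliability 0.8 (assumed), change with change has r = 0.5·√((0.8−ρ)/(1−ρ)) = 0.423, 0.387, 0.289, and power 65%, 57%, 34%. Under A, endpoint release is still significant 53% to 67% of the time.

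**5. Hypothesis 4a at n=30.**

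- An observed r of 0 has 95% CI ±tanh(1.960/√27) = ±0.36.
- A true r of 0.3 is non-significant 1 − 0.363 = 64% of the time. For 0.4 it is 1 − 0.595, about 40%.
- Power of two one-sided 5% tests at a true r of 0 is 2Φ(atanh(bound)·√27 − 1.645) − 1, floored at 0. This gives 0% for a bound of 0.30, 42% for 0.40 and 77% for 0.50. For 80% power those bounds need n of 93, 51 and 32.

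**The case against.** The strongest reply is that 4b is shorthand. It sits under an aim worded on changes, and the opening of AIMS and HYPOTHESES frames the whole study as an association between changes. Hypotheses 1b and 2b are loosely worded too: in 2b the grammatical subject is release itself, and in 1b it is unclear whether the word for change governs release. This stands. A reader might infer that 4b contradicts Aim 4, but the documents show only an ambiguity. An endpoint hypothesis could even be deliberate, since the Preliminary Data section reports NPY correlations that were stronger after training than before.

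A reader might also infer that the literal 4b always loses power. The figures do not support that. Truth B, with equal variances, forces baseline release to correlate negatively with improvement (about −0.30 to −0.19). Under truth C, endpoint release matches or beats the change score for ρ up to 0.5.

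For 4a, a reader might infer that the investigators will count non-significance as support. The plan does not say so. The pilot result described as not correlated (r=.05, p=.91) concerns resting NPY, not release, and the same section describes r=-.36 with p=.43 as a weak correlation. That is thin evidence of how 4a would be read.

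None of this supplies the missing test. The SAP still names no analysis linking NPY to any outcome.

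**Conclusion.** The point holds as a gap in the analysis plan. The growth models as described cannot test 4a or 4b, and the same sentence leaves the release hypotheses of Aims 1 and 2 without a workable test. This follows from the text and rests on no numerical assumption.

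The wording of 4b is ambiguous, not a proven contradiction. The ambiguity matters because the two readings can give different answers. With n=30, r=0.5 and ρ of 0.3 to 0.7, endpoint release is significant 60% to 74% of the time when only stable release matters, against 5% for change with change. Relative power can go either way: 18% to 35% or 57% to 94% for endpoint release, depending on the assumed truth, against at most 81% for change with change.

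For 4a, n=30 cannot support a conclusion of absence at any bound up to 0.40, where equivalence power is 42% or less. A bound of 0.50 has 77%, but ruling out only correlations that large would not support the hypothesis as worded.

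The plan should be amended. Confidence is medium, because the intended meaning of 4b is unknown and every effect-size input is assumed.

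**What to change.** 1. In the Statistical Analysis Plan, say that the growth models describe symptom change only. Say that Aim 4, and the release parts of Aims 1 and 2, are tested by correlating post-minus-pre change in rest-to-peak NPY release with post-minus-pre change in each outcome, reported as r with 95% CI. The Preliminary Data section already defines release as rest to peak. Name the cold pressor measurement to be used, since there are several per participant.
2. Reword 4b to match Aim 4. Report any endpoint-release correlation as secondary and not as evidence of change.
3. Report 4a as baseline correlations with 95% CIs and draw no conclusion of absence. State that no before/after difference will be inferred from one significant and one non-significant correlation.

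The cost is rewording two hypotheses and a few SAP sentences. The data are already collected at both CPX visits, and if change was always intended the meaning of 4b does not alter. The downsides are more modest claims for Aim 4 and a noisier measure: change in release combines four NPY values, so assay error can take power well below 81% (to 34% at reliability 0.8 and ρ=0.7, both assumed).

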## SIGNIFICANCE

The proposed R21 research study is aimed at developing an effective non-pharmacological, motivationally-based exercise training approach that can be maintained over the long-term to help individuals suffering from chronic pain and posttraumatic stress disorder (CP/PTSD) reduce and manage the symptoms of these highly comorbid disorders, as well as prevent related long-term negative health consequences and disability.

### A. Development of a Non-Pharmacological Approach to Treating CP/PTSD

The National Institute of Health (NIH) and the Veterans Health Administration (VHA) has emphasized the importance of developing novel, non-pharmacological approaches to CP management. As many as one half to three quarters of patients who present for PTSD treatment have a significant CP condition. Conversely, among persons presenting for treatment of CP, approximately 20% to 37% have PTSD. In addition, substantial research suggests that the co-prevalence of CP and PTSD negatively impacts the course of both disorders, such that individuals who experience both conditions report greater pain, affective distress and disability than individuals with either CP or PTSD alone.

Our laboratory has been examining the possible benefits of a rigorously defined, closely monitored individually tailored and motivationally based progressive exercise-training program for the CP/PTSD population. Such health behavior change paradigms are thought to be critical to improving CP in medically and psychiatrically complex populations, as well as to reducing CP-related disability and dependence on medications with high potential for abuse and morbidity, such as opioids. However, although many researchers have successfully helped patients initiate regular exercise, establishment of exercise maintenance has been difficult to achieve in both general and clinical populations. The proposed R21 investigation is therefore designed to investigate the neurobiological and related neuropsychological mechanisms by which our 3-month progressive exercise-training paradigm may foster exercise maintenance.

As discussed below, brain and plasma levels of the anti-stress, anti-nociceptive neurobiological factor, neuropeptide Y (NPY) are reduced by exposure to extreme or chronic stress, and have been found to be low in both CP and PTSD. In our previous work, we showed that maximum load exercise testing can acutely increase plasma levels of NPY in patients with CP/PTSD. Moreover, preliminary data from our current work suggest that the capacity to release NPY in response to maximum load exercise testing increases over the course of our 3-month, progressive exercise-training program in association with reductions in pain-related interference and sensitivity, as well as depression and PTSD. Moreover, the capacity for release of NPY in response to maximum load exercise testing was found to correlate with *exercise-related intrinsic motivation and self-efficacy, which have been previously shown to foster exercise maintenance*.

The proposed R21 is therefore designed to investigate hypothesized relationships between exercise-training associated augmentation of NPY system function and improved capacities for reward and self-regulation—neuropsychological capacities posited to underlie intrinsic motivation and self-efficacy, as well as predict long-term exercise maintenance.

### B. Exercise-Training Induced Augmentation of NPY System Function May Mediate Benefits in CP/PTSD

Research in rodents and humans shows that severe chronic or life-threatening stress reduces baseline plasma and central nervous system NPY levels. Effects of stress on NPY in humans and rodents are, however, individually variable. For example, exposure to extreme stress had minimal effect on NPY levels among “selected” Special Forces soldiers compared to “unselected” trainees over 3-4 weeks of selection training. In addition, NPY levels achieved at peak stress during survival training correlated negatively with dissociation and distress, and positively with military performance thought to rely on frontal lobe function. In contrast, Vietnam Veterans with severe chronic PTSD had low resting plasma NPY levels and blunted NPY responses to sympathetic system activation. Cerebrospinal fluid (CSF) NPY was also low in combat veterans with PTSD when compared to either healthy non-traumatized controls or combat-exposed healthy controls. Of note, higher resting plasma NPY was associated with decreases in PTSD symptom severity retrospectively assessed over time, and with improvements in PTSD symptoms assessed across a wait-list controlled clinical trial whether or not the active PTSD treatment was received.

Exposure to traumatic stress can lead to noradrenergic system hyperreactivity, which is the most replicated neurobiological finding across clinical studies of PTSD. As previously detailed, norepinephrine (NE) released in the prefrontal cortex (PFC) at high levels during intense stress diminishes PFC-mediated working memory, executive function and inhibition of the amygdala. NPY moderates the release of NE. Under conditions of low to moderate stress, resting levels of NPY *restrain* NE release from peripheral sympathetic neurons and in brain by activating NPY-Y2 pre-synaptic receptors. This moderates arousal and facilitates calmness. During high stress, NPY is released from sympathetic neurons and in brain; peripherally released NPY also crosses the blood brain barrier. In the brain, NPY counters the anxiogenic effects of corticotropin releasing hormone in the amygdala. In the periphery, NPY is rapidly metabolized to NPY3-36, a selective NPY-Y2 receptor agonist that

returns the firing rate of sympathetic neurons and the release of NE back to baseline. Together these effects of NPY help maintain NE release in PFC within a range that optimizes PFC function. Thus PFC-mediated inhibitory control over the amygdala and defensive reflexes can be maintained, while planned behaviors can be implemented.

NPY also has pro-reward and anti-nociceptive properties. For example, NPY prevents progression of acute pain to chronic pain, prevents opiate tolerance and withdrawal, and directly enhances dopamine-mediated reward in the nucleus accumbens. NPY is also anti-inflammatory, which too may enhance dopamine-mediated reward and reduce pain. As discussed in our review of the shared underlying neurobiology of CP and PTSD, pain contributes to amygdala reactivity, and activation of the amygdala to transmission of peripheral pain, as well as to potential impairments in frontal lobe executive function as outlined above.

*In Summary*, the capacity for NPY synthesis and/or release appears to be downregulated in PTSD and CP. We hypothesize that exercise training-induced augmentation of resting NPY levels and capacity for NPY release during stress will correlate with exercise-training induced changes in reward sensitivity, self-regulation, intrinsic motivation and self-efficacy for exercise—to thereby foster exercise maintenance.

